Précis:	The STAR-Caregivers program is an education, training, and support intervention demonstrated efficacious in reducing the behavioral and psychological symptoms of dementia. The investigators propose to test a 6-session, self-directed, online version called STAR-virtual training and follow-up (STAR-VTF) that leverages secure email within the member portal at Kaiser Permanente Washington, an online learning management system, and 6 30-minute coaching telephone calls to improve access to training, fidelity to the STAR principles, and to lower the cost of the program. Outcomes in the intervention arm will be compared to an attention control group that receives printed materials and links to online training resources but does not receive coaching.
Objectives:	Test the effectiveness of the intervention training vs. attention control in a practical clinical trial involving one hundred caregiver-person living with dementia dyads at Kaiser Permanente Washington.
Populations:	Persons living with dementia and their informal caregivers (spouses and adult children)
Site:	Kaiser Permanente Washington
Description of Intervention:	This study evaluates the effectiveness of a caregiver outreach, self-directed online training, and support program for caregivers of people with dementia who are using an antipsychotic medication to manage agitation/aggression. The Investigators will conduct a randomized trial of the caregiver program compared to a control group to measure differences in caregiver burden and discontinuation of antipsychotic medication use. The results will help in expanding access to and delivery of empirically supported behavioral health services for caregivers and persons living with dementia.
Trial Duration:	18 months
Subject Participation Duration:	6 months
Estimated Time to Complete Enrollment:	12 months

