AIM 3: Test the hypotheses that (H1) caregiver participants in STAR-VTF will have lower levels of caregiver burden at 8 weeks and 6 months compared to an attention control group; and (H2) PLWD participants in STAR-VTF will have lower rates of antipsychotic medication use at 6 months compared to control. Secondary outcomes are: caregiver depression, caregiver stress and caregiver self-efficacy. We propose to recruit 100 CG-PLWD dyads (50 per arm).

This will be the first study to test a low intensity, self-directed caregiver training program with remote support from social workers. It will also be the first study to measure changes in antipsychotic medication use by PLWD after CG training. Kaiser Permanente is an ideal setting because we have access to the complete EHR, prescription medication use, health care use, and demographic data. We will be able to identify and enroll participants in real-time using an automated data algorithm as we have done previously.(22) This study will be an important step in expanding access to training and support in a format that could be implemented within integrated delivery systems with capitated payments (i.e., Accountable Care Organizations). Growing use of EHR portals in these organizations will further increase demand for web-based care management/support. Demand will also increase as today's near-retirees, familiar with web-based applications, develop ADRD. Kaiser Permanente has pioneered such efforts and is the lead site in the Mental Health Research Network (MHRN). Findings from this study will inform a future multi-site pragmatic trial across the 13 health systems and 12 million enrollees in the MHRN.

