3.2 Secondary Outcomes

The following secondary outcome measures for the trial will be assessed:

- (1) **Antipsychotic medication Use.** Proportion of participants will at least one antipsychotic prescription refill after initial medication dispensing, using automated system pharmacy data.
- (2) **Change in caregiver depression.** Self-reported caregiver depression assessed by the 8-item Patient Health Questionnaire (PHQ-8). The PHQ-8 is an eight-item measure of depression that assesses symptoms over the last two weeks. The total sum of the 8 responses from the PHQ-8 ranges between 0 and 24 with higher scores indicating worse outcome. In general, a total of 10 or above is suggestive of the presence of depression.
- (3) **Change in caregiver self-efficacy.** Self-reported caregiver self-efficacy assessed by the Caregiver Mastery Scale. Total scores can range from 7 to 35, with higher scores reflecting greater caregiver mastery. The Caregiver Mastery Scale is a 7-item measure of self-efficacy. is a 7-item self-report scale, indicating the extent to which respondents agree (5) or disagree (1) with each item. Three items with negative statements are reverse-scored. Total scores can range from 7 to 35, with higher scores reflecting greater caregiver mastery.
- (4) **Change in caregiver stress.** Caregiver stress will be measured on the Kingston Caregiver Stress Scale. This is a 10-item measure with respondents rating the level of stress between 1 (coping fine, no stress) to 5 (extreme stress, feeling at the end of rope). Total scores vary between 10 and 50.
- (5) **Response rates for baseline, 8-week, and 6-month measures.** We will assess participants' willingness to complete study measures using the REDCap online survey by the proportion completing study measures at each time point.
- (6) **Training Completion rate.** We will report training completion rates as a measure of feasibility. Completion will be defined as viewing all 6 online training modules, conducting at least 3 phone calls with a study coach and sending at least one secure message to a study coach in the baseline to 8-week period and one message in weeks 9 through 24.
- (7) **Primary care visit rates.** Measured as the number of primary care visits per eligible study participant during the study period.

- (8) **Urgent care visit rates.** Measured as the number of urgent care visits per eligible study participant during the study period.

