7 STATISTICAL CONSIDERATIONS

7.1 *Sample Size Considerations*

We anticipate enrolling 100 PLWD-CG dyads in the trial (50 per arm), with up to 90 remaining enrolled at 6 months of follow-up (i.e., 10% lost to follow-up).

7.1.1 Statistical Power for Primary Outcome.

We calculated effect sizes for the impact of STAR-C on the Subjective Caregiver Burden scale ($d=0.77$) and the Revised Memory and Behavior Problem Checklist ($d=0.68$) based on the p-values reported for t-tests comparing the STAR-C mean with the routine medical care group mean in prior research. We will power on the RMBPC (primary outcome) and assume a loss of effect size due to the lower intensity of the intervention. Assuming an effect size of 0.65, type-I error of 0.05, power of 80%, and equal sample sizes, we will require 39 dyads in the STAR-VTF arm and 39 dyads in the control arm ($n=78$). We additionally assume it will be necessary to adjust for baseline covariate imbalance and sample attrition, thus, we will inflate our recruitment targets by 30% as we have done in the past. The final recruitment target will be 50 PLWD-CG dyads in each arm.

7.2 *Analysis Plan*

Data will be collected from project tracking systems, the Epic EMR, and other health system data systems for analysis. Baseline, 8 week, and 6 month measures will be collected via an online survey using REDCap functionality.

Data validation and quality assurance checks will be undertaken to ensure data collection during the study is sufficiently reliable.

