STAR Caregivers – Virtual Training and Follow-up

Grant Number: 1 R01AG061926-01

Principal Investigator: [name]

STATISTICAL ANALYSIS PLAN

Background/overview/purpose of study:

This is a randomized trial that tests whether receipt of telehealth training for caregivers of people with dementia can reduce utilization of antipsychotic medications, as well as improve the living conditions of both the caregiver as well as the person with dementia.

Scientific questions and outcomes:

1. Is there a change in the rate of antipsychotic medication fills within eight weeks, comparing the intervention to the control arm
 - a. Main measures: Any fill within eight weeks (binary), any refill within eight weeks (binary)
2. Is there a change in standardized scales of caregiver mastery as well as dementia symptoms.
 - a. Primary scales: Revised Memory Problem and Behavior Checklist, Caregiver Mastery, Kingston Caregiver Stress
 - b. Secondary analyses: Dementia Severity Rating Scale subscales

Predictors of interest (independent variable, could be just treatment groups, indicate type as in outcome of interest section):

All analyses will adjust for gender and age, as well as the baseline score. (e.g. the caregiver mastery analysis will adjust for caregiver mastery at baseline) Our variable of interest will be the randomization group.

Unit of analysis:

The dyad of the caregiver and person with dementia.

Other data/analytic specifics (e.g. subgroups of interest, brief discussion of missing data):

Subgroups will be exploratory analyses; we are not specifically powered on any. Missing data will be accounted for via multiple imputation via chained equations, using 100 imputed datasets.

Analytic approach, special Issues and proposed sensitivity analyses:

This is a straightforward randomized trial, so analyses will be run using ordinary least squares regression with empirical standard errors for continuous outcomes, and logistic regression for binomial outcomes. Rubin's Rules will be used to combine results across the multiple imputation datasets.

Analytic software (and version if known):

Stata, version 17.0

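### The documents rank antipsychotic use inconsistently against caregiver burden, and neither says which result decides the trial

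*SAP*

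**What the plan says.** The statements on rank fall into three groups.

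- **Medication is secondary.** Protocol 3.1 lists one primary outcome: change in burden on the RMBPC disruption subscale, at 8 weeks and 6 months. Section 3.2 opens with "The following secondary outcome measures for the trial will be assessed", and antipsychotic refill is item (1). Section 7.1.1 says "We will power on the RMBPC (primary outcome") and gives the only error rate in either document: "Assuming an effect size of 0.65, type-I error of 0.05, power of 80%, and equal sample sizes".
- **Medication stands beside burden.** Aim 3 (Protocol 2.2) states H1 for burden and then "H2) PLWD participants in STAR-VTF will have lower rates of antipsychotic medication use at 6 months compared to control". It goes on to name the secondary outcomes as depression, stress and self-efficacy, without medication. The Protocol Summary also pairs the two; the trial is "compared to a control group to measure differences in caregiver burden and discontinuation of antipsychotic medication use".
- **Medication comes first.** The SAP's purpose paragraph says that the trial "tests whether receipt of telehealth training for caregivers of people with dementia can reduce utilization of antipsychotic medications" before it mentions anything else. Its question 1 is medication: "Main measures: Any fill within eight weeks (binary), any refill within eight weeks (binary"). The RMBPC appears under question 2, as one of three scales labelled primary, with Caregiver Mastery and Kingston Caregiver Stress.

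The medication measure itself also varies: use at 6 months in Aim 3, a refill with no window in 3.2, fill and refill within eight weeks in the SAP, and an added daily versus less-than-daily analysis in 7.2.6. Neither document gives an order of testing, a division of alpha or a multiplicity rule. The SAP labels only subgroup analyses as exploratory.

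**The concern.** The two candidate outcomes can give opposite verdicts on the same data. Suppose that burden is null and any refill within eight weeks has p = 0.03. Under 3.1 the trial is negative. Under H2, or under the SAP's first question, it could be presented as positive. If burden is significant and medication null, the readings swap. Nothing in the text prevents that choice from being made once both results are known, and the several definitions of medication use widen it.

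The medication endpoint also has no stated power, so a non-significant H2 would say little about moderate effects, although its confidence interval would still inform.

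**Working it through.** **1. Reproduce the plan's own figure.** Inputs from 7.1.1: d = 0.65, alpha 0.05, power 80%, equal arms. The stated result is "we will require 39 dyads in the STAR-VTF arm and 39 dyads in the control arm". The two-sided t-test (noncentral t) gives power 79.9% at 38 per arm and 80.9% at 39, so 39 is reproduced. A one-sided 0.05 test would need only 30. The plan does not state sidedness, but its sample size implies a two-sided 5% test of burden. At d = 0.65, power is 86.2% with 45 per arm (the plan's 10% loss) and 89.6% with 50.

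**2. Assumptions for the error rates.** Neither document gives an alpha for medication, the fill or refill rates, or the correlation between tests. I assume that each test is two-sided at 0.05 and show a range of correlations. Burden is counted as one test.

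**3. Chance of at least one false positive, if either outcome may count as success.** For k independent tests this is 1 − (1 − 0.05)^k. For correlated tests I used bivariate and trivariate normal statistics with |z| > 1.96.

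| Tests | Independent | All correlations 0.5 | All correlations 0.8 |
|---|---|---|---|
| Burden + one medication measure | 1 − 0.95² = 9.75% | 9.1% | 7.8% |
| Burden + both SAP medication measures | 1 − 0.95³ = 14.3% | 12.5% | 9.8% |

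**4. Allow for nesting.** A refill cannot occur without a fill, so the two SAP measures are correlated. If refill (rate b) is nested in fill (rate a), the correlation is √[b(1−a) / (a(1−b))]. With assumed rates a = 0.9, b = 0.5 it is √(0.05/0.45) = 0.33. With a = 0.6, b = 0.5 it is √(0.20/0.30) = 0.82. At these two correlations, the chance that at least one medication measure is falsely significant is 9.5% and 7.7%. Adding an independent burden test, 0.05 + 0.95 × 0.095 = 14.0% and 0.05 + 0.95 × 0.077 = 12.3%.

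**5. Chance of a false medication-only claim.** The event of interest is burden not significant and medication significant. Its probability is the figure for either test minus the 5% for burden.

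- One measure: 9.75% − 5% = 4.75% if independent; 9.1% − 5% = 4.1% at correlation 0.5; 7.8% − 5% = 2.8% at 0.8.
- Two nested measures, independent of burden: 14.0% − 5% = 9.0% down to 12.3% − 5% = 7.3%. Simulated Wald logistic tests at 45 to 50 per arm, over several assumed nested rates, gave 6.1% to 8.8% for either measure. Multiplied by 0.95, this is 5.8% to 8.4%, slightly lower because the Wald test can be conservative at this size.

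**6. What the trial could detect on medication.** Arcsine approximation, 80% power, two-sided 0.05, with assumed control proportions of 0.50, 0.70 and 0.90:

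- 45 per arm: 0.50 to 0.22, 0.70 to 0.41, 0.90 to 0.67 (28, 29 and 23 points).
- 50 per arm: 0.50 to 0.23, 0.70 to 0.43, 0.90 to 0.68 (27, 27 and 22 points).

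**The case against.** The strongest reply is that the sections meant to designate outcomes agree. Sections 3.1, 3.2 and 7.1.1 all put burden first and alone. Aim 3 never calls H1 and H2 co-primary, and a secondary outcome may carry a hypothesis. The SAP never says that question 1 outranks question 2, and it attaches the word primary to the RMBPC, not to medication. If the designating sections govern, the primary outcome is not in doubt and no error inflation attaches to it.

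Much of this stands, and it rules out three stronger readings that a reader might infer.

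- **That the SAP reverses the protocol's order.** The evidence is question numbering and phrase order only. With the RMBPC labelled primary, the SAP is ambiguous, not reversed.
- **That medication is tested at full alpha.** This is inferred from silence. The 0.05 belongs to the burden power calculation, and the SAP states no alpha, so every error rate above is conditional.
- **That a burden-null trial would be called positive on medication at about twice 5%.** The 9–10% figure is for either outcome being falsely positive, and it includes trials in which burden is the false positive. For a medication-only claim, one measure gives about 4–5%. Only two measures come near twice 5%, and nesting keeps them below it.

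The reply does not remove the conflict. Aim 3 leaves medication off its secondary list within the same protocol that lists it as secondary, and no statement says that 3.1 prevails over the SAP.

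**Conclusion.** The point holds as an inconsistency in rank that leaves the trial's deciding result open. The conflict is textual and needs no assumption.

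The size does need assumptions: each test at two-sided 0.05, and either outcome allowed to count as success. The chance of at least one false positive is then about 9–10% for burden plus one medication measure (correlation 0.5 to 0) and about 12–14% with both SAP measures, falling to about 10% if all three correlate at 0.8. A false medication-only claim has a chance of about 4–5% with one measure (correlation 0.5 to 0) and about 7–9% with two nested measures independent of burden (correlation between them 0.33 to 0.82). If 3.1 is taken to govern, burden is the sole primary and none of these rates applies to the primary verdict, but the documents do not say so.

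**What to change.** 1. State in the SAP that RMBPC burden, as in Protocol 3.1, is the sole primary outcome and alone decides the trial at two-sided 0.05. Name one of 8 weeks or 6 months as the deciding time point; without that, the burden test cannot play this role.
2. Name one medication measure and one window as the secondary outcome for H2, after reconciling Aim 3 (6 months), 3.2 (no window) and the SAP (eight weeks). Make the other SAP measure supportive.
3. Report medication as a secondary estimate with a 95% confidence interval, with no confirmatory claim if burden is not significant. Formal testing of medication after a significant burden result is optional.
4. Reword Aim 3, the SAP purpose sentence and the order of the SAP questions to match.

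This needs no extra data or participants, and the burden test keeps its full 0.05 (power 86.2% at 45 per arm, 89.6% at 50). Splitting alpha 0.025/0.025 between burden and one medication measure would instead lower burden power to 78.7% and 83.3%. The cost of the proposed change is that a medication effect without a burden effect could not be claimed as confirmed. The sponsor should accept that knowingly, since the SAP's purpose sentence puts medication first.

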4 TRIAL DESIGN

We will conduct a parallel, two-arm pragmatic clinical trial comparing the intervention and attention control groups. The follow up period for the trial will be 6 months.

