5 STUDY ENROLLMENT AND WITHDRAWAL

5.1 *Inclusion and Exclusion Criteria for Persons Living with Dementia*

The investigators will identify and recruit PLWD-CG dyads in which the PLWD has filled a new prescription for an antipsychotic medication. The study programmer will identify potential PLWD-CG dyads using an automated data algorithm that queries claims data and electronic health record (EHR) data on a weekly basis.

Because we will enroll dyads, there are inclusion/exclusion criteria for both persons living with dementia and their caregivers.

Persons with dementia inclusion criteria:

- Aged \geq 65 years
- Diagnosis of Alzheimer's Disease or related dementia (ADRD)
- Expected to live \geq 6 months from enrollment

Persons with dementia exclusion criteria:

- A diagnosis of bipolar disorder or schizopreniform disorder
- The primary care physician's opinion is that the person with dementia is expected to live less than 6 months.
- Primary language is not English (patient requires a translator).

5.2 *Inclusion and Exclusion Criteria for Caregiver Subjects*

Potentially eligible caregivers are identified by the family contact information in the electronic medical record.

Caregiver inclusion criteria:

- Aged \geq 21 years
- Lives with person with dementia or within 8 miles
- Provides at least 8 hours of care per week

Caregiver exclusion criteria:

- Diagnosis of Alzheimer's Disease or related disorders.
- Caregiver is not the spouse or adult child of the person living with dementia
- Primary language is not English (caregiver requires a translator).

5.3 ***Randomization Assignment Procedures***

5.3.1 ***Randomization Procedures***

The study biostatistician will create a randomization schedule and this will be uploaded into a REDCap database. Caregivers who remain eligible for the study after screening will be randomized within REDCap following the pre-set randomization schedule. All eligible caregiver-patient dyads will be block randomized to ensure comparable numbers of dyads enrolled in each study arm. Caregivers will be categorized according to age (<75 years, >=75 years), sex, and spouse/non-spouse.

R, an open-source statistical computing software, will be used to generate an even number of control and intervention assignments within each block.

5.3.2 ***Blinding***

Study staff will be blinded to study arm when verifying subject eligibility.

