7.2.2 Aim 1. Feasibility/Acceptability

We will measure response rates for follow-up data collection using the online survey functionality in REDCap. We will use descriptive statistics to characterize response rates by study arm and demographic characteristics. We will use generalized estimating equations (GEE) with a working correlation matrix to estimate a logistic regression model for response vs. non-response. We will estimate separate models for the 8-week and 24-week outcome periods. Models will be adjusted for PLWD stage of dementia (DSRS), PLWD FAQ score, PLWD age and sex, caregiver relationship (spouse, non-spouse), caregiver age and sex, caregiver highest level of education attained, PLWD residential status (living with caregiver full-time versus not) and study arm.

7.2.3 Feasibility/Acceptability - Completion of Training.

We will use descriptive statistics to characterize completion rates by study arm and demographic characteristics. We will use generalized estimating equations (GEE) with a working correlation matrix to estimate a logistic regression model for completion vs. non-completion. Models will be adjusted for PLWD stage of dementia (DSRS), PLWD FAQ score, PLWD age and sex, caregiver relationship (spouse, non-spouse), caregiver age and sex, and caregiver highest level of education attained, and study arm.

7.2.4 Assess the feasibility and acceptability from the payer perspective.

We will use descriptive statistics to characterize the effort required by coaches to facilitate caregiver training. These measures are (1) time reading secure messages, (2) number of exchanges per message thread, (3) number of ad hoc phone calls required (i.e., other than the 6 scheduled calls).

7.2.5 Primary Care, Urgent Care and Emergency Department Use.

We will use longitudinal, generalized estimating equations (GEE) to estimate a Poisson regression model for adjusted mean monthly visit rates (separately by visit type) in the STAR-VTF arm compared to the attention control arm in the 6 months following randomization. Models will be adjusted for PLWD stage of dementia (DSRS), PLWD FAQ score, PLWD age and sex, caregiver relationship (spouse, non-spouse), caregiver age and sex, and caregiver highest level of education attained, and study arm. We will use the robust sandwich estimator to calculate standard errors to account for repeated (i.e. 6 monthly) observations within people and the misspecified variance in the Poisson model.

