7.2.6 Effect of STAR-VTF on CG burden and PLWD antipsychotic medication use.

We will measure overall caregiver burden using the Revised Memory and Problem Behavior Checklist (RMPBC). We will use GEE with a working correlation matrix to estimate the regression model, using robust sandwich estimators to calculate standard errors accounting for within person correlation. We will adjust for baseline pre-randomization covariates: PLWD stage of dementia (DSRS), PLWD FAQ score, PLWD age and sex, caregiver relationship (spouse, non-spouse), caregiver age and sex, and caregiver highest level of education attained.

We will use generalized estimating equations (GEE) with a working correlation matrix to estimate a logistic regression model for refill (versus no refill) of the initial antipsychotic medication. Models will be adjusted for PLWD stage of dementia (DSRS), PLWD FAQ score, PLWD age and sex, caregiver relationship (spouse, non-spouse), caregiver age and sex, and caregiver highest level of education attained, study arm. We will again use GEE with a working correlation matrix to estimate a logistic regression model for daily versus “less than daily” use of antipsychotic medication (as reported to the coach). Models will again be adjusted for pre-randomization variables listed above.

7.2.7 Caregiver depression, stress and self-efficacy.

Caregiver depression will be measured using the PHQ-8. Caregiver self-efficacy will be measured using the Caregiver Mastery Scale. Caregiver stress will be measured using the Kingston Caregiver Stress Scale. We will again use GEE to compare the mean PHQ-8, CMS and Kingston scores in the STAR-VTF and attention control arms. Models will be adjusted for pre-randomization variables as above.

7.3 *Handling of Missing Data*

Preventing missing data is superior to statistical treatment. We will make every effort to collect data on all study participants. If there are substantial missing data or significant loss-to-follow-up, we will use inverse probability weighting(23) to rebalance the STAR-VTF and attention control group. Inverse probability weights are used to rebalance groups on prognostic factors when the treatment and control groups become unbalanced over time, post-randomization, due to study drop out. If we find intermittent missing data, we will instead use multiple imputation(24) via chained equations to address the problem, using at least 10 imputed datasets and combining results using Rubin's rules.

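### H2 concerns antipsychotic use at 6 months, but the SAP's only antipsychotic measures stop at eight weeks with no stated start, and the protocol's own refill and daily-use models do not measure use at 6 months either

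*SAP*

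**What the plan says.** - **Hypothesis.** Protocol 2.2, Aim 3 (H2): "PLWD participants in STAR-VTF will have lower rates of antipsychotic medication use at 6 months compared to control". Section 4 adds: "The follow up period for the trial will be 6 months".
- **SAP.** The first scientific question is about antipsychotic fills, and its main measures are "Any fill within eight weeks (binary), any refill within eight weeks (binary"). No later antipsychotic measure is listed, and no origin is given for the eight weeks.
- **Protocol outcome.** Section 3.2(1) counts people with "at least one antipsychotic prescription refill after initial medication dispensing, using automated system pharmacy data". This has a start, the initial dispensing, but no end.
- **Protocol models.** Section 7.2.6 plans a "logistic regression model for refill (versus no refill) of the initial antipsychotic medication", again with no window. It adds a second logistic model comparing daily with "less than daily" use, taken from what the coach is told, also with no time point.
- **Entry.** Section 5.1 recruits dyads in which the "PLWD has filled a new prescription for an antipsychotic medication", so every person with dementia has a fill before randomization.
- **Contrast.** For visit rates, section 7.2.5 gives both origin and window: "compared to the attention control arm in the 6 months following randomization". Nothing similar is written for antipsychotic use.

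**The concern.** H2 is one of the two named hypotheses of Aim 3, and reducing antipsychotic use is the first purpose the SAP states. An analyst who follows the SAP exactly will report early dispensing and nothing at 6 months. A null result at eight weeks could then be read as no effect on antipsychotic use, although only early fills were examined.

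The protocol and SAP measures can also classify the same person differently, and neither document says which one governs. Unless that is settled beforehand, the choice could be made after the results are known.

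**Working it through.** No sample size, use rate or refill rate is given for H2, so there is no H2 figure to reproduce. The only sample-size figure, 39 dyads per arm at effect size 0.65, is for the RMBPC. A two-sided two-sample t-test at 5% and 80% power gives 38.14, which rounds up to 39. This point does not touch it.

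**1. Each planned analysis against H2** (any antipsychotic use, at 6 months, by arm)

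| Analysis | Start | End | Measures use at 6 months? |
|---|---|---|---|
| SAP, fill and refill | not stated | eight weeks | No: wrong time point |
| Protocol 3.2(1) and 7.2.6, refill | initial dispensing, before randomization | not stated | No: cumulative even if the end is taken as 6 months; 7.2.6 also limits it to the initial drug |
| Protocol 7.2.6, daily use | not stated | not stated | No: no time point, and coach-reported |

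On the last row, scheduled coaching calls are described only for the intervention arm (6.1, 6.6). Control caregivers have the consent and orientation contact and three scripted messages (5.3.2, 5.5). How comparable reports would be obtained in both arms is not stated.

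**2. What eight weeks covers, under each possible origin**
- From randomization: 8/26 = 31% or 8/24 = 33% of follow-up. The six modules are taken one per week (6.5), so at most about 8 − 6 = 2 weeks follow the training.
- From the index fill, counting that fill: everyone enrolled has one, so the any-fill measure is 100% in both arms and carries no information.
- From the index fill, excluding it: part of the window falls before randomization. The steps in between are a weekly data query, chart review, a required prescriber reply, a mailed letter and a screening call (6.2). The documents do not give the lag.

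**3. Illustration of misclassification, on assumed values.** Let the supply be S days, the index fill d days before randomization, and refills on time at day kS − d. Neither S nor d appears in the documents.
- *Continuing user missed by the SAP measures, counted from randomization.* With S = 90 the first refill is on day 90 − d, which exceeds 56 for d = 0 to 33. At d = 33 the fills are on days 57 and 147, and supply lasts to day 237: a user at day 180 with no fill in days 1 to 56. With S = 30 the first refill after randomization is always by day 30, so this error does not occur.
- *Stopper counted as a user.* With S = 30, d = 10 to 29, and one refill then stopping, supply ends on day 60 − d, that is day 50 to day 31. Of 180 days, 130 to 149 (72% to 83%) have no supply, yet the person counts as a user on both the SAP and the protocol measures.
- *Refill before randomization.* With S = 30 and d = 35, the refill falls on day 30 − 35 = −5. The protocol definition would still count it as an outcome event.

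These cases show that both kinds of error are possible. They do not show how often either would happen.

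**The case against.** The strongest reply is that the protocol is not silent. H2 gives 6 months, section 4 sets a 6-month follow-up, and section 7.2.6 is the antipsychotic analysis, so the natural reading is any refill during follow-up. Nothing says that the SAP replaces it. A reader might therefore go too far in concluding that later antipsychotic use goes unexamined altogether, or that two-thirds of follow-up is ignored. The documents do not support either statement: the protocol's refill analysis may well run to 6 months, and the one-third share holds only if the SAP's clock starts at randomization. What survives is narrower. Any refill by 6 months is not use at 6 months, and its clock starts before randomization.

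Other replies have partial force:
- Counting the index fill is an unlikely intention for a between-arm measure. True, but the text does not exclude it.
- Effects could begin before training ends, since problem solving is taught in the second module. That supports eight weeks as an early measure, not as the test of H2.
- Deaths should be limited because entry requires expected survival of at least 6 months (5.1, 6.2). They can still occur, and no rule says how to score them for this outcome.
- Supply covering a single day also misclassifies: a slightly late refill looks like stopping. This stands, and is why a grace period is needed.
- No section says that days' supply is captured. This also stands, so the fix must offer an alternative.

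**Conclusion.** The point holds. The SAP as written does not estimate H2, and neither protocol model measures antipsychotic use at 6 months. The conclusion rests on the text alone and needs no assumption about prescribing.

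Its size can be stated only in part. If the eight weeks run from randomization, they cover 31% to 33% of follow-up and at most about two weeks after the modules. The proportion misclassified cannot be derived, because the documents give no days' supply, fill rate, stopping rate or lag to randomization.

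A reader might infer that the trial's main result is compromised. It is not: antipsychotic use is listed as secondary (3.2) and the trial is powered on the RMBPC (7.1.1). The damage is confined to H2. This should be fixed before outcomes are examined.

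**What to change.** In the SAP and in protocol 3.2(1) and 7.2.6, name one analysis as the test of H2:

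- **Endpoint.** A binary measure of use of any antipsychotic, switches included, at 6 months after randomization, from the automated pharmacy data, with randomization as time zero. One option, if days' supply is held, is dispensed supply covering day 180 with a prespecified grace period. Otherwise, use any fill in a prespecified window ending at 6 months.
- **Model.** Logistic regression in all randomized dyads by assigned arm, with one adjustment set in both documents. At present the protocol lists dementia severity, function, ages, sexes, relationship and education, while the SAP lists gender, age and a baseline score that has no evident counterpart for a fill outcome.
- **Deaths.** Report deaths before 6 months by arm, prespecify one way of handling them, and give the alternative as a sensitivity analysis.
- **Existing measures.** Keep the eight-week fill and refill measures, counted from randomization and with the two terms distinguished, and the coach-reported model, all as supportive only.

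The cost is wording in two documents and a little more programming. Pharmacy data are already planned, and section 5.4 keeps antipsychotic measurement going after caregiver withdrawal, so no new participants or surveys are needed. Whether days' supply is available must be checked. The remaining weakness is that dispensing is an imperfect proxy when the drug is taken less often than daily, a pattern section 7.2.6 anticipates.
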